### 9.3 Populations for Analyses

For purposes of analysis, the following populations are defined:

Population	Description
Enrolled	All participants who sign the ICF
Safety population for the study 19764	Participants enrolled into the study and received at least 1 dose of study intervention. Participants will be analyzed according to the intervention they actually received. The safety population will be used for the safety analysis.
Intent-to-treat (ITT) population for the study 19764	All safety participants who have injection/bleeding data from the EPD and CRF for at least 3 months. The ITT population will be used for the efficacy analysis.
Safety population for pooled analysis	The safety population for the pooled analysis will consist of the safety population of this study as defined above and the safety populations of studies 13024 Part A and 15912.
Efficacy population for pooled analysis	The efficacy population for the pooled analysis will consist of the ITT population of this study as defined above and the extension ITT populations of studies 13024 Part A and 15912.

### 9.4 Statistical Analyses

The statistical analysis plan will be developed and finalized before first patient first visit (FPFV) and will describe the participant populations to be included in the analyses, and procedures for accounting for missing, unused, and spurious data. This section is a summary of the planned statistical analyses of the primary and secondary endpoints.

#### 9.4.1 Efficacy Analyses

The secondary objective of the study is to assess clinical efficacy. All efficacy analyses will be performed on the ITT population with a treatment period of at least 3 months.

The following efficacy variables will be analyzed:

- Annualized bleeding rate for joint and spontaneous bleeds
- Percentage of participants with 0 spontaneous bleeds within a 6-months treatment period
- Annualized number of total bleeds (sum of spontaneous bleeds and trauma bleeds)
- Incremental recovery will be summarized
- Total number of exposure per year will be documented in patient diaries and summarized
- Extent of exposure to study intervention during the study in terms of exposure days (ED) and injection characteristics (number of units, consumption dose/kg per participant/year, reason for treatment, type, location and severity of bleeds and response to treatment) will be summarized for each participant receiving any amount of drug.

Other pre-specified exploratory endpoints will be described in the statistical analysis plan finalized before database lock.

An integrated efficacy analysis will be done based on combined data from this study and studies 13024 Part A and 15912. Results will be provided by age groups.

#### **9.4.2 Safety Analyses**

All safety analyses will be performed on the Safety Population. Laboratory findings, adverse events, concomitant medications, vital signs, and medical history data will be provided in subject listings.

Those participants who were given at least one dose of Jivi will be valid for the safety analysis. Inhibitor development will be summarized by time point and presented in subject listings. The purpose of the listing is to delineate the clinical factors which may be positively associated with development of the inhibitor. Confirmation of positive inhibitor titers (Bethesda  $\geq 0.6$  BU/mL) will require repeat measurement. If the repeated inhibitor result is  $<0.6$  BU without intervention, the inhibitor is not confirmed and should not be reported as an SAE. Inhibitors will be classified as being either low titer ( $\geq 0.6$  BU/mL and  $\leq 5$  BU/mL) or high titer based upon persistence of an inhibitor  $>5$  BU. Participants will also be monitored for other antibodies against the drug substance Jivi and/or PEG. Proportions of participants with inhibitor or antibodies will be presented in an overview table.

Laboratory values and vital signs will be summarized. Individual listings of AEs (including AEs as reported, start, duration, severity, relation to study drug) will be provided. The incidence of treatment-emergent adverse events (AEs) will be summarized using the Medical Dictionary for Regulatory Activities (MedDRA). An AE will be considered treatment-emergent if it starts after first injection and not later than 7 days after last injection of Jivi.

Integrated safety analyses will be done based on combined data from this study and studies 13024 Part A and 15912. Summary tables for demographics, baseline characteristics (including gene defect), medical history (including family history of hemophilia and history of inhibitor), concomitant medications, extent of exposure, treatment-emergent AEs, and laboratory findings will be provided. Results will be provided by age groups.

#### **9.5 Interim Analyses**

An optional interim analysis will be performed, if needed for regulatory submission or publication purposes, after all participants have been treated for 6 months for assessment of the main safety (inhibitor development) and efficacy endpoints. The risk for inhibitor development is highest during the first 20-50 ED. After this timepoint, the study would be continued according to the study design and protocol.

## 10. Supporting Documentation and Operational Considerations

### 10.1 Appendix 1: Regulatory, Ethical, and Study Oversight Considerations

#### 10.1.1 Regulatory and Ethical Considerations

- This study is a post-approval regulatory requirement according to the EMA Guidelines for a new marketed FVIII and will be conducted in accordance with the protocol and with the following:
  - Consensus ethical principles derived from international guidelines including the Declaration of Helsinki and Council for International Organizations of Medical Sciences (CIOMS) International Ethical Guidelines
  - Applicable International Council for Harmonization (ICH) Good Clinical Practice (GCP) Guidelines
  - Applicable laws and regulations
- The protocol, protocol amendments, ICF, SmPC, and other relevant documents (e.g., advertisements) must be submitted to an IRB/IEC by the investigator and reviewed and approved by the IRB/IEC before the study is initiated.
- Any amendments to the protocol will require IRB/IEC approval before implementation of changes made to the study design, except for changes necessary to eliminate an immediate hazard to study participants.
- The investigator will be responsible for the following:
  - Providing written summaries of the status of the study to the IRB/IEC annually or more frequently in accordance with the requirements, policies, and procedures established by the IRB/IEC
  - Notifying the IRB/IEC of SAEs or other significant safety findings as required by IRB/IEC procedures
  - Providing oversight of the conduct of the study at the site and adherence to requirements of ICH guidelines, the IRB/IEC, and all other applicable local regulations

#### 10.1.2 Financial Disclosure

Investigators and sub-investigators directly involved in the treatment or evaluation of study participants will provide the sponsor with sufficient, accurate financial information as requested to allow the sponsor to submit complete and accurate financial certification or disclosure statements to the appropriate regulatory authorities. Investigators are responsible for providing information on financial interests during the course of the study and for 1 year after completion of the study.

### 10.1.3 Informed Consent Process

- The investigator and/or delegate will explain the nature of the study to the participant and answer all questions regarding the study, based on the patient informed consent. The patient informed consent will contain all relevant information on the study.
- Participants must be informed that their participation is voluntary. Participants will be required to sign a statement of informed consent that meets the requirements of local regulations, ICH guidelines, where applicable, and the IRB/IEC or study center.
- The medical record must include a statement that written informed consent was obtained before the participant was enrolled in the study and the date the written consent was obtained. The authorized person obtaining the informed consent must also sign the ICF.
- Participants must be re-consented to the most current version of the ICF(s) during their participation in the study.
- A copy of the ICF(s) must be provided to the participant.

Participants who are rescreened are required to sign a new ICF.

### 10.1.4 Data Protection

- Participants will be assigned a unique identifier by the sponsor. Any participant records or datasets that are transferred to the sponsor will contain the identifier only; participant names or any information which would make the participant identifiable will not be transferred.
- The participant must be informed that his personal study-related data will be used by the sponsor in accordance with local data protection law. The level of disclosure must also be explained to the participant.
- The participant must be informed that his/her medical records may be examined by Clinical Quality Assurance auditors or other authorized personnel appointed by the sponsor, by appropriate IRB/IEC members, and by inspectors from regulatory authorities.

### 10.1.5 Dissemination of Clinical Study Data

Result Summaries of Bayer's sponsored clinical trials in drug development phases II, III and IV and Phase I studies in patients are provided in the Bayer Trial Finder application after marketing authorization approval in line with the position of the global pharmaceutical industry associations laid down in the "Joint Position on the Disclosure of Clinical Trial Information via Clinical Trial Registries and Databases". In addition results of clinical drug trials will be provided on the publicly funded website [www.ClinicalTrials.gov](http://www.ClinicalTrials.gov) and EU Clinical Trials Register in line with the applicable regulations.

Bayer commits to sharing upon request from qualified scientific and medical researchers patient-level clinical trial data, study-level clinical trial data, and protocols from clinical trials

in patients for medicines and indications approved in the United States (US) and European Union (EU) on or after January 01, 2014 as necessary for conducting legitimate research.

All Bayer-sponsored clinical trials are considered for publication in the scientific literature irrespective of whether the results of the clinical trials are positive or negative.

### **10.1.6 Data Quality Assurance**

- All participant data relating to the study will be recorded on electronic CRF unless transmitted to the sponsor or designee electronically (e.g., laboratory data). The investigator is responsible for verifying that data entries are accurate and correct by physically or electronically signing the CRF.
- The investigator must maintain accurate documentation (source data) that supports the information entered in the CRF.
- The investigator must permit study-related monitoring, audits, IRB/IEC review, and regulatory agency inspections and provide direct access to source data documents.
- Monitoring details describing strategy (e.g., risk-based initiatives in operations and quality such as Risk Management and Mitigation Strategies and Analytical Risk-Based Monitoring), methods, responsibilities and requirements, including handling of noncompliance issues and monitoring techniques (central, remote, or on-site monitoring) are provided in the Monitoring Plan.
- The sponsor or designee is responsible for the data management of this study including quality checking of the data.
- The sponsor assumes accountability for actions delegated to other individuals (e.g., Contract Research Organizations).
- Study monitors will perform ongoing source data verification to confirm that data entered into the CRF by authorized site personnel are accurate, complete, and verifiable from source documents; that the safety and rights of participants are being protected; and that the study is being conducted in accordance with the currently approved protocol and any other study agreements, ICH GCP, and all applicable regulatory requirements.
- Records and documents, including signed ICFs, pertaining to the conduct of this study must be retained by the investigator for 15 years after study completion unless local regulations or institutional policies require a longer retention period. No records may be destroyed during the retention period without the written approval of the sponsor. No records may be transferred to another location or party without written notification to the sponsor.

### **10.1.7     Source Documents**

- Source documents provide evidence for the existence of the participant and substantiate the integrity of the data collected. Source documents are filed at the investigator's site.
- Data reported in the eCRF that are transcribed from source documents must be consistent with the source documents or the discrepancies must be explained. The investigator may need to request previous medical records or transfer records, depending on the study. Also, current medical records must be available.
- Definition of what constitutes source data can be found in a source document checklist.
- Patient reported outcome variables which are transmitted via EPD are considered source documentation.

### **10.1.8     Study and Site Closure**

The sponsor designee reserves the right to close the study site or terminate the study at any time for any reason at the sole discretion of the sponsor. Study sites will be closed upon study completion. A study site is considered closed when all required documents and study supplies have been collected and a study-site closure visit has been performed.

The investigator may initiate study-site closure at any time, provided there is reasonable cause and sufficient notice is given in advance of the intended termination.

Reasons for the early closure of a study site by the sponsor or investigator may include but are not limited to:

- Failure of the investigator to comply with the protocol, the requirements of the IRB/IEC or local health authorities, the sponsor's procedures, or GCP guidelines
- Inadequate recruitment of participants by the investigator
- Discontinuation of further study intervention development

### **10.1.9     Publication Policy**

- The results of this study may be published or presented at scientific meetings. If this is foreseen, the investigator agrees to submit all manuscripts or abstracts to the sponsor before submission. This allows the sponsor to protect proprietary information and to provide comments.
- The sponsor will comply with the requirements for publication of study results. In accordance with standard editorial and ethical practice, the sponsor will generally support publication of multicenter studies only in their entirety and not as individual site data. In this case, a coordinating investigator will be designated by mutual agreement.
- Authorship will be determined by mutual agreement and in line with International Committee of Medical Journal Editors authorship requirements.

## 10.2 Appendix 2: Clinical Laboratory Tests

- The tests detailed in [Table 10-1](#) will be performed by the central laboratory
- All laboratory analyses will be performed at central laboratories. Investigators will be provided with a laboratory manual for instructions on how to collect and process samples.
- Protocol-specific requirements for inclusion or exclusion of participants are detailed in [Section 5](#) of the protocol.
- Additional tests may be performed at any time during the study as determined necessary by the investigator or required by local regulations locally or centrally as needed.

**Table 10-1: Protocol-Required Safety Laboratory Assessments**

Laboratory Assessments	Parameters								
Hematology	Platelet Count	White blood cell (WBC) count with Differential							
	Erythrocytes								
	Hemoglobin								
	Hematocrit								
Clinical Chemistry	Blood urea nitrogen (BUN)	Potassium	Aspartate Aminotransferase (AST)	Total bilirubin					
	Creatinine	Sodium	Alanine Aminotransferase (ALT)	Total Protein					
	Albumin								
Routine Urinalysis	
 
• pH, glucose, protein, blood, ketones, bilirubin, urobilinogen, leukocyte esterase by dipstick
 
								
Renal Biomarkers	
 
• The urine samples for assessment of renal safety in participants with long term polyethylene glycol (PEG) exposure will include biomarkers (e.g. total protein and albumin [as albumin/creatinine ratio], and potentially beta-2microglobulin and Kim-1)
 
								
Other Laboratory Tests	
 
• Serology: HIV antibody for screening purpose only
 
• Immunogenicity testing including antibodies to Jivi and/or PEG and FVIII inhibitor.
 
• FVIII level
 
• PEG level in plasma
 
 
All routine study-required laboratory assessments will be performed by a central laboratory, with the exception of some samples sent by central lab to independent specialty labs for required tests of FVIII level, FVIII inhibitors, antibodies to Jivi and/or PEG (anti-drug antibodies [ADA]) and PEG
								

Investigators must document their review of each laboratory safety report.

## 10.3 Appendix 3: Adverse Events: Definitions and Procedures for Recording, Evaluating, Follow-up, and Reporting

### 10.3.1 Definition of AE

#### AE Definition

In a clinical study, an AE is any untoward medical occurrence (ie, any unfavorable and unintended sign [including abnormal laboratory findings], symptom or disease) in a subject or clinical investigation subject after providing written informed consent for participation in the study. Therefore, an AE may or may not be temporally or causally associated with the use of a medicinal (investigational) product.

A surgical procedure that was planned prior to the start of the study by any physician treating the subject should not be recorded as AE (however, the condition for which the surgery is required may be an AE).

In the following differentiation between medical history and AEs, the term “condition” may include abnormal, eg, physical examination findings, symptoms, diseases, laboratory values.

- Conditions that started before signing of informed consent and for which no symptoms or treatment are present until signing of informed consent are recorded as medical history (eg, seasonal allergy without acute complaints, abnormal laboratory finding at screening).
- Conditions that started before signing of informed consent and for which symptoms or treatment are present after signing of informed consent, at unchanged intensity, are recorded as medical history (eg, allergic pollinosis).
- Conditions that started or deteriorated after signing of informed consent will be documented as adverse events.

**Note:** Any bleeding event occurring during the study will not be documented as an AE, because this event is captured in the assessment of efficacy. However, if the bleed requires hospitalization or fulfills another seriousness criterion, it must be reported as a Serious Adverse Event (SAE) (Section 10.3.2).

Bleeding events treated with Jivi and recorded in the EPD do not need to be documented as AEs because they are already captured. However, occurrence of traumatic injury and other bleeds should follow standard AE reporting procedures. Any bleed requiring hospitalization or fulfilling another seriousness criterion must be reported as a SAE (Section 10.3.2).

---

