#### Each injection of Jivi:

- a. Date and time
- b. Injection record
- c. Individual vial number (bar code scan from vial label or manual entry) and units administered
- d. Reason for treatment

Prophylaxis

Spontaneous bleed first treatment

Trauma bleed first treatment

Follow-up treatment

Other

Injections of Jivi as part of protocol mandated visits and procedures will be recorded on the respective CRF pages.

All bleeding episodes (regardless if treated or not, or treated at home or under medical supervision) as well as any potential treatment with other hemophilia drugs will be recorded in the EPD:

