**Bleeding episode (onset)**

- a. Date and time of onset
- b. Type of bleed (spontaneous, trauma; joint, muscle, skin/mucosal, internal, other)
- c. Location
- d. Intensity (mild, moderate, severe)
- e. Treated [yes/no];
  - if "yes": Date and time
  - Product used: Jivi or other
  - Doses

If Jivi is used for the treatment of a bleeding episode, the response to treatment (excellent, good, moderate, poor, too early to tell) must to be recorded

For guidance to the participant, the following definitions for response to treatment are suggested:

**Excellent:** Abrupt pain relief and/or improvement in signs of bleeding with no additional injection administered

**Good:** Definite pain relief and/or improvement in signs of bleeding, but possibly requiring more than one injection for complete resolution

**Moderate:** Probable or slight improvement, with at least one additional injection for complete resolution

**Poor (or None):** No improvement or condition worsens.

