### 8.3.6 Disease-Related Events and/or Disease-Related Outcomes Not Qualifying as AEs or SAEs

The following disease related outcome is common in participants with hemophilia A and can be serious/life threatening:

- Bleeding event

Any bleeding event, regardless if treated or not, occurring during the study will not be documented as an AE, because this is captured in the assessment of efficacy.

Because these events are typically associated with the disease under study, they will not be reported according to the standard process for expedited reporting of AEs. These events will be recorded in the EPD.

*NOTE: However, if the bleed fulfills the criterion for an SAE (e.g. results in hospitalization), then the event should be recorded and reported as an SAE (see Section 10.3.2).*

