**Events NOT Meeting the AE Definition**

---

- Any clinically significant abnormal laboratory findings or other abnormal safety assessments which are associated with the underlying disease, unless judged by the investigator to be more severe than expected for the participant’s condition.
- The disease/disorder being studied or expected progression, signs, or symptoms of the disease/disorder being studied, unless more severe than expected for the participant’s condition.
- Medical or surgical procedure (e.g., endoscopy, appendectomy): the condition that leads to the procedure is the AE.
- Situations in which an untoward medical occurrence did not occur (social and/or convenience admission to a hospital).
- Anticipated day-to-day fluctuations of pre-existing disease(s) or condition(s) present or detected at the start of the study that do not worsen.
- Any bleeding event occurring during the study will not be documented as an AE, because this is captured in the assessment of efficacy. However, if the bleed fulfills the criterion for an SAE (e.g. results in hospitalization), then the event should be recorded and reported as an SAE.

---

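### The protocol gives opposite AE reporting instructions for non-serious bleeds not treated with Jivi, so TEAE counts can differ between sites

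*Protocol*

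**What the plan says.** Three places in the protocol exempt bleeds from AE documentation unless they are serious:

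- Section 8.3.6: "Any bleeding event, regardless if treated or not, occurring during the study will not be documented as an AE".
- The Note under AE Definition in section 10.3.1: "Any bleeding event occurring during the study will not be documented as an AE, because this event is captured in the assessment of efficacy".
- The list headed Events NOT Meeting the AE Definition in section 10.3.1: "Any bleeding event occurring during the study will not be documented as an AE, because this is captured in the assessment of efficacy".

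The paragraph directly after the Note in 10.3.1 sets a narrower exemption: "Bleeding events treated with Jivi and recorded in the EPD do not need to be documented as AEs because they are already captured". It continues: "However, occurrence of traumatic injury and other bleeds should follow standard AE reporting procedures". It closes with serious bleeds: "Any bleed requiring hospitalization or fulfilling another seriousness criterion must be reported as a SAE".

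Protocol 8.1.1 has every bleed entered in the EPD, treated or not. The bleed record includes a treated yes/no item and the field "Product used: Jivi or other".

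In the SAP, section 6.4 makes an AE treatment-emergent if it starts after the first injection and within 7 days of the last. It has no rule on bleed terms. SAP 6.2 provides a listing of all untreated bleeds in this study.

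**The concern.** Consider a non-serious bleed that the participant leaves untreated, or treats with another product, and enters in the EPD. A site that follows 8.3.6, the Note or the exclusion list records no AE. A site that follows the paragraph after the Note finds that the bleed fails the treated-with-Jivi condition and sends it to AE reporting. Both sites are following current protocol text.

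TEAEs are a secondary endpoint under the primary safety objective. They feed the overview, non-serious and maximum-intensity tables in SAP 6.4 and, through SAP 4.1, the pooled safety results. If sites follow different paragraphs, part of the TEAE count reflects site convention and not what happened to participants. The study is multicenter and single-arm, so no control group would share and reveal such a difference.

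**Working it through.** The plan gives no figure to reproduce. The check is mainly a comparison of texts.

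**Step 1. Apply each rule to each kind of bleed.**

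| Bleed | 8.3.6, the Note and the exclusion list | Paragraph after the Note in 10.3.1 |
|---|---|---|
| Non-serious, treated with Jivi, in EPD | Not an AE | Not an AE |
| Non-serious, untreated, in EPD | Not an AE | AE reporting |
| Non-serious, treated with another product, in EPD | Not an AE | AE reporting |
| Non-serious, missing from EPD | Not an AE | AE reporting |
| Serious | SAE | SAE |

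The rules agree in the first and last rows and conflict in the three between.

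**Step 2. Test readings that would remove the conflict.**

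- The other bleeds are the serious ones. This fails because the next sentence deals with serious bleeds separately.
- The other bleeds are those missing from the EPD. The reason given for the exemption, that the bleeds are already captured, fits this reading. It does not explain the added condition of treatment with Jivi, and a bleed missing from the EPD is still exempt under the blanket rule. By design the set should also be empty, since the EPD takes "All bleeding episodes (regardless if treated or not, or treated at home or under medical supervision").
- Traumatic injury means the injury and not the bleed. This works for that half of the sentence. The conflict comes from the words about other bleeds.

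**Step 3. Ask whether such bleeds are foreseen.** Protocol 6.1 says that bleeds after Visit 2 will be treated with Jivi, which narrows the set. It does not empty it. The EPD has fields for untreated bleeds and for another product. Protocol 7.1.1 allows other FVIII around elective major surgery. SAP 4.5 counts untreated bleeds among all bleeds, and SAP 6.2 lists them. Screening bleeds are treated with the previous product (Protocol 6.5) but precede the first injection, so they cannot be TEAEs.

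**Step 4. Look for a tie-breaker.** SAP 6.4 has a time window only. SAP 4.5 has rules for counting bleeds for efficacy and none for bleed terms in the AE data.

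**Step 5. Scale per participant.** The protocol plans 25 to 30 treated participants. If TEAE incidence is the share of participants with at least one TEAE, one participant whose only TEAE is such a bleed moves it by:

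- 1/30 = 3.3 percentage points
- 1/25 = 4.0 percentage points

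In the pooled set of Protocol 9.2, 134 + 73 + 25 = 232, so the shift is 1/232 = 0.4 percentage points. A participant who has another TEAE does not change overall incidence, although the rows for the bleed term and its organ class would still change.

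**The case against.** The blanket rule appears three times, once with explicit mention of untreated bleeds, and its rationale is clear: bleeds are captured under efficacy. The opposing instruction is one sentence worded as *should*. A sensible site may follow the majority text, and CRF instructions or the monitoring plan, which are not among the documents, may already settle it. The analyses are descriptive, untreated bleeds are listed anyway, and no bleed in the EPD is lost.

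This limits the weight of the point but does not remove it. A rule stated three times and contradicted in the paragraph after one of those statements is still ambiguous. The listing of untreated bleeds shows them as efficacy data and does not correct a TEAE table.

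Two stronger readings are tempting, and the documents do not support either.

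- A reader might infer that sites will in fact report differently. The text shows only that they can.
- A reader might multiply an assumed bleed rate by follow-up time and conclude that dozens of TEAEs are at stake. The documents give no rate of bleeds not treated with Jivi, and Protocol 6.1 suggests that there may be few. Follow-up to 100 exposure days depends on the regimen, so one duration cannot be applied to everyone. A count of events would also overstate the effect on a participant-level incidence, because repeat bleeds in one man count once.

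**Conclusion.** The contradiction stands. It is in the current protocol text, and nothing else in the protocol or the SAP resolves it. It covers non-serious bleeds that are untreated, treated with another product or missing from the EPD.

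The total effect on TEAE incidence cannot be estimated. The supportable size is the shift per affected participant in Step 5, which assumes participant-level incidence and no other TEAE in that participant.

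A reader might also suspect that the main results are affected. They are not. The inhibitor endpoint comes from the laboratory, the annualized bleeding rate uses recorded bleeds whatever their AE status, and serious bleeds are SAEs under every version of the rule. The point should be corrected, but it does not threaten the study's primary conclusion.

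**What to change.** **Protocol.** Reconcile 8.3.6, the Note and the exclusion list with the paragraph after the Note by replacing that whole paragraph. Deleting only the sentence on other bleeds is not enough, because the narrower exemption before it would remain and still imply that other bleeds are not exempt. One possible text follows the rule already stated three times: a non-serious bleed recorded in the EPD is not an AE, whether treated or not; an associated injury is reported as its own AE; a serious bleed is an SAE.

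The same text should say that loss-of-efficacy and hypersensitivity events are still reported as AEs. Protocol 8.3.7 makes both AEs of special interest, section 10.3.1 requires AE reporting for lack of efficacy, and section 8.2.1 names unexpected bleeding among the signs of loss of efficacy.

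**SAP 6.4.** Present TEAEs with and without non-serious bleed terms entered as AEs, for this study and for the pool, and list those terms. Do not remove any event reported as loss of efficacy or as an AE of special interest. A blanket removal of bleed terms could strip out such events.

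**Cost.** One replaced paragraph, a notice to sites and a short SAP addition. No new data are needed. If site practice can no longer be changed, the SAP addition alone would make the TEAE tables interpretable.
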